1. INTRODUCTION

Study KAN-101-03 is a multi-center, double-blind, placebo-controlled Phase 2a study to examine whether KAN-101 confers protection from gluten challenge (GC)-induced histological changes in the duodenum and to further evaluate the safety/tolerability of KAN-101 in adult patients (≥ 18 years) with celiac disease (CeD).

This SAP provides the detailed methodology for summary and statistical analyses of the data collected in study KAN-101-03. This document may modify the plans outlined in the protocol; however, any major modifications of the primary endpoint definition or its analysis will also be reflected in a protocol amendment.

1.1. Study Objectives, Endpoints, and Estimands

Study objectives, corresponding endpoints, and estimands are provided in the Table 2 below.

Table 2 Objectives, Endpoints, and Estimands

Objectives	Endpoints	Estimands
Primary:	Primary:	Primary:
Assess the ability of KAN-101 to attenuate GC-induced changes in duodenal histology as measured by changes in villus-height:crypt depth (Vh:Cd) ratio after a 2-week GC.	Changes from baseline in Vh:Cd ratio as assessed by esophagogastroduodenoscopy (EGD) with biopsy after 2-week GC (at Day 29).	Estimand 1: a hypothetical estimand (Section 1.1.1).
Secondary:	Secondary:	Secondary:
Examine the impact of KAN-101 on biomarker response (interleukin-2 [IL-2]) in peripheral blood following GC	IL-2 change from Day 15 (first day of GC) pre GC to Day 15 post GC.	Estimand 2: a hypothetical estimand (Section 1.1.2).
Determine the effects of KAN-101 on histologic features (intraepithelial lymphocytes [IELs] density) in duodenum biopsies following 2-week GC.	Changes from baseline in IEL density in duodenum biopsy after 2-week GC (at Day 29)	Estimand 3: a hypothetical estimand (Section 1.1.2).
Assess the safety and tolerability of KAN-101 in participants with CeD.	Incidence and severity of treatment emergent adverse events (TEAEs) as assessed by the Common Terminology Criteria for Adverse Events (CTCAE) v6.0 (or higher).	Not applicable.
	Incidence and titer of KAN-101 anti-drug antibodies (ADA).	Not applicable.
Assess the pharmacokinetics (PK) of multiple doses of KAN-101 in participants with CeD.	Plasma concentration of KAN-101, and associated KAN-101 parameters: AUC_{inf} , AUC_{last} , C_{max} , T_{max} and $t_{1/2}$	Not applicable.

Table 2 Objectives, Endpoints, and Estimands

Objectives	Endpoints	Estimands
Tertiary/Exploratory:	Tertiary/Exploratory:	Tertiary/Exploratory:
Evaluate changes in histological features (Marsh-Oberhuber score) after 2-week GC	Changes from baseline in Marsh-Oberhuber score after 2-week GC (at Day 29)	Not applicable.
Assess the impact of KAN-101 administration on the incidence of CeD symptoms before and during GC as measured using CDSD v2.1.	Changes from baseline in symptoms PROs including: CDSD v2.1, PGIC and PGIS over time.	Not applicable.
Assess whether KAN-101 affects the incidence and/or titer of post-GC celiac serology.	Change from baseline in incidence and titer of tTG IgA and DGP IgG at Day 42.	Not applicable.

1.1.1. Primary Estimand

Estimand 1: The primary estimand is the hypothetical estimand, which estimates the treatment effect of KAN-101 vs placebo (PBO) for change from baseline in Vh:Cd ratio. It includes the following 5 attributes:

- Population: Participants who receive all 3 doses of study intervention and complete at least 7 days of GC and do not receive prohibited medications.
- Variable: Vh:Cd ratio change from baseline at Day 29.
- Treatment conditions: KAN-101 or PBO.
- Intercurrent Events: Events are addressed in the analysis set definition.
- Population level summary: The least-squares mean (LSM) difference of the change from baseline in Vh:Cd ratio between KAN-101 and PBO.

1.1.2. Secondary Estimand

Estimand 2 is the hypothetical estimand, which estimates the treatment effect of KAN-101 vs PBO for IL-2. It includes the following 5 attributes:

- Population: Participants who receive all 3 doses of study intervention, complete GC at Day 15 and do not receive prohibited medications.
- Variable: log transformed IL-2 change from pre GC to post GC at Day 15.
- Treatment condition: KAN-101 or PBO.
- Intercurrent Events: Events are addressed in the analysis set definition.

- Population level summary: The LSM difference of the change from pre GC to post GC at Day 15 (log transformed) between KAN-101 and PBO.

[figure not shown]
Estimand 3 is the hypothetical estimand, which estimates the treatment effect of KAN-101 vs PBO for change from baseline in duodenal IEL density. It includes the following 5 attributes:

- Population: Participants who receive all 3 doses of study intervention and complete at least 7 days of the 2-week GC and do not receive prohibited medications .
- Variable: IEL change from baseline at Day 29.
- Treatment conditions: KAN-101 or PBO.
- Intercurrent Events: Events are addressed in the analysis set definition.
- Population level summary: The LSM difference of the change from baseline in IEL between KAN101 and PBO.

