### 6.9.2. Permitted During the Study

Hormonal contraceptives that meet the requirements of this study are allowed to be used in participants who are WOCBP (see [Appendix 4](#)).

HRT use by postmenopausal women is permitted if they meet requirements in [Appendix 4](#).

Any other medication that is considered necessary for the participant's welfare that is not expected to interfere with the evaluation of KAN-101 may be given at the discretion of the investigator and documented on the CRF.

In cases involving concomitant therapies whose predicted interference with KAN-101 is unknown to the investigator, Pfizer should be contacted for discussion.

Any medication (including over-the-counter or prescription medications, vitamins, and/or herbal supplements) that the participant receives after enrollment through the last study visit must be recorded on the CRF. Participants should report any changes to permitted medications during the study to the investigator as soon as they occur. Medication changes must be documented in the participant's record and CRF.

Participants being treated for IBS symptomology will be allowed to continue current treatment (eg, dicyclomine) unless the drug is specifically prohibited; participants should be

CONFIDENTIAL

on a stable dose for at least 4 weeks prior to entry and remain on a stable dose throughout the study.

Antidiarrheal (eg, loperamide), antiemetics (eg, metoclopramide or ondansetron), or acetaminophen may be used for symptomatic treatment if warranted unless the drug is specifically prohibited. These symptomatic treatments are optionally allowed as pre-treatment to study intervention administration at Day 4 and Day 7 at investigator discretion. If given at a study visit, use must be recorded on the CRF.

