### 9.2. Estimands

#### 9.2.1. Primary Estimand

Estimand 1 will be used for the primary endpoint main analysis.

**Estimand 1:** The primary estimand is the hypothetical estimand, which estimates the treatment effect of KAN-101 vs placebo for change from baseline in the ratio of Vh:Cd under the scenario of no intercurrent events. It includes the following 5 attributes:

- **Population:** Participants who receive all 3 doses of study intervention and complete at least 7 days of GC;
- **Variable:** the ratio of Vh:Cd change from baseline to Day 29;
- **Treatment condition:** KAN-101 or placebo;

- **Intercurrent events:** Prohibited medication. All data collected after any intercurrent events will be excluded;
- **Population-level summary:** The LSM difference of the change from baseline in Vh:Cd between KAN-101 group and placebo.

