#### 9.2.1.1. Secondary Estimands

**Estimand 2** is hypothetical, which estimates the treatment effect of KAN-101 compared with placebo for IL-2 under the scenario of no intercurrent events. It includes the following 5 attributes:

- **Population:** Participants who complete all 3 doses of study intervention and complete at least 7 days of GC;
- **Variable:** log transformed IL-2 change from pre GC to post GC at Day 15 (first day of GC);
- **Treatment condition:** KAN-101 or placebo;
- **Intercurrent events:** prohibited medication, incomplete GC on Day 15. All data collected after any intercurrent events will be excluded;
- **Population-level summary:** the LSM difference (log transformed) of the change from pre GC to post GC at Day 15 (first day of GC) between KAN-101 group and placebo.

**Estimand 3** is the hypothetical estimand, which estimates the treatment effect of KAN-101 vs placebo for change from baseline in duodenal IEL density under the scenario of no intercurrent events. It includes the following 5 attributes:

- **Population:** Participants who complete all 3 doses of study intervention and complete at least 7 days of GC;
- **Variable:** IEL change from baseline to Day 42;
- **Treatment conditions:** KAN-101 or placebo;
- **Intercurrent Events:** Prohibited medication. All data collected after any intercurrent events will be excluded;
- **Population level summary:** The LSM difference of the change from baseline in IEL between KAN-101 and placebo.

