3. ANALYSIS SETS

For purposes of analysis, the following analysis sets are defined:

Analysis Set	Description
Enrolled	All participants who sign the ICD.
Biomarker Analysis Set (BAS)	All participants who are randomly assigned to study intervention, receive any portion of study intervention, and have completed the GC on Day 15, without prohibited medications. Participants will be analyzed according to the intervention they are randomized.
Full analysis set (FAS)	All participants who are randomly assigned to study intervention, receive all 3 doses of study intervention, and complete at least 7 days of the 2-week GC without prohibited medications. Participants will be analyzed according to the intervention they are randomized.

Analysis Set	Description
Per protocol set (PPS)	The PPS will include all participants from the FAS who complete all 14 days of the 2-week GC and biopsies, and without major protocol violations that might affect the evaluation of the effect of study intervention on the primary endpoint. The PPS will be used in sensitivity analyses of the primary and secondary endpoints. Specific reasons for warranting exclusion from this population will be documented prior to database lock.
Safety analysis set (SAS)	All participants who receive any portion of study intervention. Participants will be analyzed according to the intervention they actually received.
PK analysis set (PKAS)	All participants who receive any portion of study intervention and have at least one concentration value.

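### The SAP turns prohibited medication into an undated exclusion of the whole participant, so read literally it discards IL-2 and biopsy results obtained before the medication, which the protocol keeps

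*SAP*

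**What the plan says.** **Protocol.** Section 9.2.1 (Estimand 1) gives the intercurrent event and its handling as "Prohibited medication. All data collected after any intercurrent events will be excluded". Section 9.2.1.1 (Estimand 2) has "prohibited medication, incomplete GC on Day 15. All data collected after any intercurrent events will be excluded", and Estimand 3 follows Estimand 1. None of the three protocol populations contains a medication condition.

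**SAP estimands.** Section 1.1.1 defines the Estimand 1 population as participants who have all three doses and "complete at least 7 days of GC and do not receive prohibited medications". Section 1.1.2 does the same for Estimand 3, and for Estimand 2 requires that participants "receive all 3 doses of study intervention, complete GC at Day 15 and do not receive prohibited medications". The intercurrent-event attribute of each estimand is replaced by a pointer: "Events are addressed in the analysis set definition".

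**SAP analysis sets.** Section 3, where the pointer leads, requires FAS members to "complete at least 7 days of the 2-week GC without prohibited medications" and BAS members to "have completed the GC on Day 15, without prohibited medications". Neither definition says when the medication must have been taken.

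**SAP section 7** declares that prohibited medication has moved into the set definitions, but states no period.

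**What is prohibited, and what is recorded.** Protocol 6.9.1 bars the listed therapies during the study, and vaccines until 4 weeks after the last dose. Protocol 6.9.2 says that any medication a participant "receives after enrollment through the last study visit must be recorded on the CRF".

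**The concern.** A rule about data has become a rule about people, and its time reference was lost on the way. Under the protocol, a value measured before the medication stays in. Under the SAP as worded, the participant goes, along with values that the medication could not have affected.

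Membership of the primary analysis set then depends on events after the outcome was measured. Such events follow randomisation and may be related to treatment or to the response to gluten, so removing these participants serves no purpose under a hypothetical strategy and could unbalance the arms. Because medication is recorded to the last visit, any such event will be in the database and the programmer will have to act on it. In a trial of 26 per arm, the text should fix the primary set.

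**Working it through.** **1. The two rules by time of first prohibited medication.** Nominal schedule: doses on Days 1, 4 and 7, first gluten challenge (GC) and IL-2 samples on Day 15, biopsy on Day 29, last visit on Day 42. The SAP column takes the condition as applying at any time in the study.

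| First prohibited medication | Result | Protocol | SAP, literal |
|---|---|---|---|
| Day 1 to before the 4-hour Day 15 sample | IL-2 | excluded | excluded |
| After that sample to Day 42 | IL-2 | **kept** | **excluded** |
| Day 1 to before the biopsy | Vh:Cd, IEL | excluded | excluded |
| After the biopsy to Day 42 | Vh:Cd, IEL | **kept** | **excluded** |

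For example, a systemic steroid first given on Day 20 removes the IL-2 value measured on Day 15. A vaccine on Day 32 removes the biopsy taken on Day 29.

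**2. Why medication before the biopsy makes no difference to Vh:Cd.** There is one post-baseline biopsy, the model is an ANCOVA on change from baseline (SAP 4.2.1), and missing efficacy values are not imputed (Protocol 9.4.1.2, SAP 4.3). Excluding the biopsy value and excluding the participant leave the same observations in the model.

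**3. Length of the exposed periods.**
- IL-2: SAP Table 8 accepts a first GC on Days 14 to 17, so 42 − 17 = 25 to 42 − 14 = 28 days.
- Vh:Cd and IEL: 42 − 29 = 13 days after a Day 29 biopsy, plus the rest of Day 29.
- Vaccines: barred to Day 7 + 28 = Day 35, so for them the period after the biopsy ends at about Day 35.

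**4. The other possible reading.** Taken alone, the FAS sentence could attach the medication condition to the challenge days. Medication on Days 1 to 14 would then exclude nobody, although the protocol excludes the later biopsy. But under that reading the FAS would admit people whom the Estimand 1 and 3 populations shut out, since in SAP 1.1.1 and 1.1.2 the condition stands by itself.

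**5. Size, as an illustration.** Inputs from SAP 1.3: difference 0.5, SD 0.5, 26 per arm, final two-sided level 0.049. Power is from the noncentral t distribution with n1 + n2 − 2 degrees of freedom and noncentrality 0.5 / (0.5 × √(1/n1 + 1/n2)).
- Plan's own figure: 26/26, noncentrality 3.606, power 94.2% at level 0.05 and 94.1% at 0.049. The stated 94% reproduces.
- One result lost per arm (25/25): noncentrality 3.536, power 93.3%.
- Two lost per arm (24/24): noncentrality 3.464, power 92.2%.
- From the dropout scenario in Protocol 9.6 (20% and 40%, about 21 and 16 evaluable): 83.2% at 0.049, falling to 80.8% with one more lost per arm (20/15) and 78.3% with two (19/14).

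The numbers lost are assumptions. The documents give no rate of prohibited medication use.

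**The case against.** The strongest reply has four parts.

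- *The SAP may depart from the protocol, and did so openly.* Protocol section 9 allows this, SAP section 7 declares the move, and the SAP version history shows that it was deliberate. That stands: a reader might infer a concealed change, and the documents do not support it. Section 7 does not, however, give the period or say that values measured before the medication are now lost.
- *The text is not evenly balanced between two readings.* This also stands. A reader might infer that the primary set is wholly indeterminate. The estimand populations make the condition free-standing, the BAS sets it off with a comma, and Protocol 6.9.1 speaks of the whole study. All three lean towards any time, which makes over-exclusion the main defect and the challenge-only reading secondary.
- *The safety-set analyses keep every result.* Vh:Cd, IEL and IL-2 are also analysed in the SAS, which has no medication condition, so they partly show what the exclusion does. They do not restore the protocol rule, because they also keep values collected after the medication. The PPS inherits the FAS condition.
- *The primary endpoint is barely exposed.* For Vh:Cd only first use after the biopsy matters. This is correct and limits the size. Under the literal reading, a participant counted at the interim could leave the FAS before the final analysis, but no efficacy stopping decision follows from the interim, and its details are left to a separate plan.

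**Conclusion.** The point holds as a defect of wording with a real, probably small, consequence. The SAP replaces a dated rule on data by an undated rule on participants, and its literal meaning removes valid results because of later events: IL-2 over about 25 to 28 days, Vh:Cd and IEL over about 13 days after a Day 29 biopsy. A reader might infer that the primary result is biased or the trial underpowered. The documents support neither: they give no event frequency, nothing shows the direction of any selection, and one or two losses per arm from 26/26 cost about one to two points of power.

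This rests on reading the condition as applying throughout the study, on the nominal visit days, and on one post-baseline value per endpoint without imputation. It should be corrected before database lock.

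**What to change.** Amend SAP 1.1.1, 1.1.2, 3 and 7 in one of two ways.

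1. **Restore the protocol's rule**: exclude an endpoint value only if it was collected after prohibited medication, and take the medication condition out of the populations and sets.
2. **Date the condition for each endpoint.**
   - IL-2, in the BAS and wherever IL-2 is analysed in the PPS: no prohibited medication from first dose up to the actual 4-hour post-GC sample.
   - Vh:Cd and IEL, in the FAS and PPS: none from first dose up to the actual post-GC biopsy. Actual dates matter because SAP Table 7 accepts biopsies from Day 22 to Day 43.
   - The biopsy cut-off must not carry over to IL-2 in the PPS, or a Day 20 medication would still remove a Day 15 value.

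Under the second option, say that starting at first dose is the SAP's choice, since the protocol estimands give no start, and that washout breaches before dosing are eligibility deviations (exclusion criterion 14).

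Under either option, state how medication recorded on the first GC date without a clock time is treated, because Protocol 6.9.2 requires recording but does not mention times. For the patient-reported outcomes, which also use the FAS, exclude only values after the medication, or say that whole-participant exclusion is intended.

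The cost is SAP text and a date comparison for each endpoint. Medication is already recorded to the last visit, so the only possible gap is clock times on the first GC day.

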1.2. Study Design

Study KAN-101-03 is a multi-center, double-blind, PBO-controlled Phase 2a study to examine whether KAN-101 confers protection from GC-induced histological changes in the duodenum and to further evaluate the safety/tolerability of KAN-101 in adult patients (≥ 18 years) with CeD. Approximately fifty-two patients (26 patients per arm) will be randomized 1:1 to 0.6 mg/kg KAN-101 (Arm 1) or PBO (Arm 2).

Figure 1 Study Design Schema

1.3. Sample Size

A sufficient number of participants will be screened to achieve approximately 52 treated participants (26 per study arm). The sample size calculation is based on the primary efficacy estimand and its endpoint, changes from baseline in the ratio of Vh:Cd at Day 29 visit. With

an overall 2-sided type I error rate of 5%, the study will have approximately 94% power under a sample size of 26 participants per arm to detect a treatment difference in LSM of 0.50 in change in ratio of Vh:Cd between treatment arms, assuming that the common standard deviation is 0.5 and the difference between the means is 0.5. To adjust for multiple looks, the O'Brien-Fleming adjustment is applied to control overall type I error rate to ensure that the overall Type I error rate remains at 5%. The interim analysis will be evaluated at significance level 0.003 and the final look will be evaluated at significance level 0.049.

2. ENDPOINTS AND BASELINE VARIABLES: DEFINITIONS AND CONVENTIONS

2.1. Primary Endpoint

- Change from baseline in Vh:Cd ratio as assessed by EGD with biopsy after 2-week GC (at Day 29).

The biopsy will be performed at screening and Day 29, or ET visit. The Baseline is the last non-missing Vh:Cd ratio at screening.

2.2. Secondary Endpoints

- GC IL-2 change from Day 15 (first day of GC) pre-GC to Day 15 post GC.

GC IL-2 will be log transformed prior to calculating the change.

- Change from baseline in IEL density in duodenum biopsy after 2-week GC (at Day 29).

The biopsy will be performed at screening and Day 29, or ET visit. The Baseline is the last non-missing IEL density at screening.

- Incidence and severity of TEAEs as assessed by the CTCAE.

See [Section 2.5.1](#).

- Incidence and titer of KAN-101 ADA.

Positive of ADA will be assessed at Days 1, 7, 29, 42 or early termination (ET) visit.

- Plasma concentration of KAN-101, and associated KAN-101 parameters: AUC_{inf}, AUC_{last}, C_{max}, T_{max} and t_{1/2}.

Parameter	Definition	Method of Determination
AUC _{last}	Area under the plasma concentration-time profile from time 0 to the time of the last quantifiable concentration (C _{last})	Linear/Log trapezoidal method
AUC _{inf}	Area under the plasma concentration-time profile from time 0 extrapolated to infinite time	AUC _{last} + (C _{last} /K _{el}), where C _{last} is the predicted plasma concentration at the last quantifiable time point estimated from the log-linear regression analysis
C _{max}	Maximum plasma concentration	Observed directly from data
T _{max}	Time to first occurrence of C _{max}	Observed directly from data.
t _{1/2} ^a	Terminal elimination half-life	Log _e (2)/K _{el} , where K _{el} is the terminal Phase rate constant calculated by a linear regression of the loglinear - concentration time- curve. Only those data points judged to describe the terminal log-linear decline will be used in the regression

- a. If data permits.

2.3. Exploratory Endpoints

- Changes from baseline in Marsh-Oberhuber score assessed via EGD with biopsy after 2-week GC.
- The biopsy will be performed at screening and Day 29, or ET visit. Baseline is the last non-missing Marsh-Oberhuber score at screening.
- CSDS

- CDSD is a patient reported outcome (PRO) questionnaire collected daily. The version 2.1 includes 5 severity items and 3 frequency supplement questions (see [Appendix 2.2](#)) that will be collected daily.
 - CDSD Total Score is the sum of all 5 severity items. The CDSD Weekly Average Total Score will be calculated , for details on the calculation see below, Section [5.3.2](#) and [Appendix 2.2](#).
 - The CDSD Gastrointestinal (GI) Domain Score is the sum of items 1-4. The CDSD Weekly Average Gastrointestinal (GI) Domain Score will be calculated, for details on the calculation see below, Section [5.3.2](#) and [Appendix 2.2](#) .
 - For CDSD Nausea score and vomiting frequency, in addition to weekly average score, 3-day average will be derived as well (every 3 days start from Day 15 GC until Day 41). If 2 observations are missing, the 3-day average score will not be calculated. Day 15 Nausea score and vomiting frequency will be analyzed as well.
- For CDSD Total score, GI Domain score, individual severity item and frequency supplement question, the Baseline value is the average of most recent 7-day interval scores before Day 1 (not include Day 1) with at least 4 days with non-missing scores, and will be used as the baseline to calculate the change from baseline to the 1-day, 3-day average and weekly average. If there are ≥ 4 days missing scores in any 7-day interval before Day 1, the baseline value is set as missing.
- For post-baseline weekly average score calculation, Week 1 is from Day 1 to Day 7, Week 2 is from Day 8 to the day before Day 15 GC, Week 3 is from the day after Day 15 GC to Day 21. The number of days for Week 2 and Week 3 maybe equal to, less than, or greater than 7. See Section [5.3.2](#) for the details. The weekly average score is the weekly sum score divided by the number of days with non-missing in that week. If daily scores are missing for more than half of total days in a specific week, the average score is missing for that week.
- Change from baseline at each timepoint = observed (or derived as described above) value at each timepoint – baseline.
- The observed value and the change in PGIS
- PGIS is a PRO questionnaire designed to assess the patient's impression of disease severity over the past week (see [Appendix 2.3](#)) that is collected at baseline (Day 1), Day 15, 29, 42, or ET visit.
- Change from baseline at each timepoint = observed value at each timepoint – baseline. Baseline is the last non-missing value up to Day 1.
- The observed value in PGIC

- PGIC is a PRO questionnaire designed to assess the patient's impression of the overall change in participant's celiac disease since receiving study intervention (see [Appendix 2.4](#)) that will be collected at Days 15, 29, 42, or ET visit.
- Change from baseline in incidence and titer of tTG IgA and DGP IgG at Day 42.
- Other exploratory biomarkers may be analyzed at a later date.

